### 5 Investigational Plan

#### 5.1 Overview

This is a single-center, open-label, investigator-initiated trial evaluating the effects of IMG-7289 administered orally once daily in patients with essential thrombocythemia (ET). The therapeutic goal for the treatment of ET is to inhibit the activity of LSD1 in hematopoietic cells for only a fraction of the 24-hour dosing cycle, sufficient to reduce the production of platelets and granulocytes, respectively, whose over-production characterizes the condition. Considerations for a safe and therapeutic starting dose include chronic toxicology studies in conjunction with the clinical experience of the patients who have received IMG-7289 to date in IMG-7289-CTP-101 and -102. Using all of the information available in conjunction with the therapeutic goal for the treatment of myeloproliferative neoplasms, an IMG-7289 starting dose of 0.6 mg/kg QD has been selected. Refer to Sections 3.4 and 3.5 for additional detail on the rationale for the starting dose and dose regimen.

This study consists of two treatment periods: the Initial Treatment Period (ITP), followed by the Additional Treatment Period (ATP). In the ITP, patients will be treated daily for 169 days. The ATP offers treatment to qualifying patients for an additional 169 days. The ATP is iterative and may repeat as long as the patient continues to qualify. Patients not deriving clinical benefit, or who achieve complete remission (CR) or partial remission (PR) and subsequently relapse (Section 12.4) the equivalent of treatment failures, will discontinue IMG-7289 and undergo follow-up.

All patients will undergo follow-up period visits, including an End-of-Treatment (EoT) visit on the day of last dose or as soon as possible thereafter, a pre-End-of-Study (EoS) visit approximately 14 days post last dose, and an End-of-Study (EoS) visit approximately 28 days post last dose. Patients that do not enter the ATP, or discontinue early, will undergo follow-up beginning with an EoT visit. A patient will be considered to have completed the study if they have been dosed with IMG-7289 for the full 24 weeks.

Patients will be followed closely throughout the study for both Adverse Events (AEs) and signs of toxicity by frequent monitoring of clinical signs and symptoms as well as safety labs. Pharmacodynamic effects will be closely monitored by frequent hematology assessments of peripheral blood, and requisite bone marrow aspirates and biopsies. Throughout dosing, transfusions may be administered if needed in accordance with standard institutional guidelines.

#### 5.2 Initial Treatment Period

Using dose titration, the dose of IMG-7289 will be adjusted in each patient to that dose that provides sufficient exposure to safely inhibit thrombopoiesis for a fraction of the dosing cycle (designated as the  $D_{pi}$ ). Treatment will begin on Day 1 at the IMG-7289  $D_s$  of 0.6 mg/kg QD for all patients, with dose-titration contingent on the comparison of hematology values from the prior visit. Up-titration may begin on ITP Day 29 and occur no more frequently than every 4 weeks from the previous up- or down-titration. Down-titration can be made at any time in the best interest of the patient. Up-titration will be made in increments of 0.2 mg/kg/d, and down-titration in decrements of 0.1 or 0.15 mg/kg/d.

The dose of IMG-7289 needed to reduce platelets to the target range is anticipated to be up to approximately 2 mg/kg QD; however, this is not the upper limit for titration purposes as the dose needed to achieve a therapeutic effect will vary among patients and may change over time. The platelet titration target expected to be associated with a clinically significant therapeutic effect is:  $\geq 200$  to  $\leq 400$  k/ $\mu$ L (200-400 x  $10^9$ /L).

During the ITP, patients will initially return for study assessments weekly for the first 8 weeks (ITP Days 8, 15, 22, 29, 36, 43, 50 and 57), at least bi-weekly for 8 weeks (ITP Days 71, 85, 99 and 113) and then monthly for 8 weeks (ITP Days 141 and 169). It is anticipated that by Week 8 (Day 57) patients will have achieved a stable dose, with weekly visits no longer necessary. For safety purposes, weekly visits may continue at the PI's discretion (note: bi-weekly visits may also continue post Day 113), if necessary. On Day 169 bone marrow sampling is required. At the Day 169 visit, a 'qualification' assessment will be made to determine whether the patient is deriving clinical benefit and safely tolerating IMG-7289. Such patients qualify for entry into the ATP, a transition which should occur without interruption in dosing. Patients not deriving clinical benefit, or who achieve complete remission (CR) or partial remission (PR) and subsequently relapse (Section 12.4) the equivalent of treatment failures, will discontinue IMG-7289 and undergo End of Treatment (EoT), pre-End of Study (pre-EoS) and End of Study (EoS) visits.

### **5.3 Additional Treatment Period for Qualifying Patients Only**

In the ATP, treatment may continue for an additional 169 days in those patients deriving clinical benefit, as determined by the Principal Investigator. Qualifying patients will return for study assessments monthly (ATP Days 1, 29, 57, 85, 113, 141 and 169). It is anticipated that patients continuing in the ATP will have already achieved a stable dose, with bi-weekly visits no longer necessary. For safety purposes, bi-weekly visits may continue at the PI's discretion, if necessary. On Day 169 of every other ATP (i.e., ATP2 Day 169, ATP4 Day 169) for as long as the patient continues to qualify for treatment, patients will undergo optional bone marrow sampling. At the Day 169 visit, a 'qualification' assessment will be made to determine whether the patient is continuing to derive clinical benefit. Such patients thereby qualify for re-entry into the ATP, which is iterative; patients may continue to receive IMG-7289 for as long as they continue to qualify. Patients not deriving clinical benefit will discontinue IMG-7289 and undergo EoT, pre-EoS and EoS visits.

### **5.4 Inclusion and Exclusion Criteria**

#### **5.4.1 Inclusion Criteria**

Inclusion criteria are as follows:

1. Age  $\geq 18$  years.
2. Diagnosis of Essential Thrombocythemia per World Health Organization (WHO) diagnostic criteria for myeloproliferative neoplasms ([Arber et al., 2016](#)).
3. Patients who are intolerant or resistant to hydroxyurea per ELN criteria, or in the Investigator's judgment are not candidates for available approved therapy. The ELN definitions of resistance/intolerance to HU requires the fulfillment of at least one of the following criteria:
  - Platelet count  $>600 \times 10^9$ /L after a daily dose of at least 2 g HU for at least 3 months (2.5 g/day in patients with a body weight over 80 kg);
  - Platelet count  $>400 \times 10^9$ /L and WBC  $<2.5 \times 10^9$ /L at any dose of HU;
  - Platelet count  $>400 \times 10^9$ /L and hemoglobin  $<10$ g/dL at any dose of HU
  - Presence of unacceptable HU-related non-hematologic toxicities, including fever, mucocutaneous manifestations or leg ulcers.
4. Requires treatment in order to lower platelet counts based on the Clinically Relevant IPSET-Thrombosis Guidelines.
5. Platelet count  $>450 \times 10^9$ /L pre-dose Day 1.
6. Peripheral blast count  $\leq 5\%$  pre-dose Day 1.
7. ANC  $\geq 0.5 \times 10^9$ /L pre-dose Day 1.
8. Fibrosis Score  $<$ grade 2, as per a slightly modified version ([Arber et al., 2016](#)) of the European Consensus Criteria for Grading Myelofibrosis, ([Thiele et al., 2005](#)).

9. Life expectancy > 36 weeks.
10. Able to swallow capsules.
11. Amenable to spleen size determination, bone marrow evaluations (in the ITP only, optional in the ATPs), and peripheral blood sampling during the study.
12. Must have discontinued ET therapy at least 2 weeks (4 weeks for interferon) prior to study drug initiation.
13. Agrees to use an approved method of contraception from Screening until 28 days after last administration of the study drug. Acceptable methods of birth control include: birth control pills, depo-progesterone injections, a vaginal hormonal contraceptive ring, a barrier contraceptive such as a condom with spermicide cream or gel, diaphragms or cervical cap with spermicide cream or gel, or an intrauterine device (IUD).
14. If male, agrees not to donate sperm or father a child for at least one month after the last dose of the study medication.

#### **5.4.2 Exclusion Criteria**

Exclusion criteria are as follows:

1. Greater than 3 separate transfusion episodes over the last 6 months and/or any transfusion over the last 4 weeks.
2. Eastern Cooperative Oncology Group (ECOG) questionnaire score of 3 or greater.
3. Currently pregnant or planning on being pregnant in the following 6 months or currently breastfeeding.
4. Currently residing outside the United States.
5. History of splenectomy.
6. Unresolved treatment related toxicities from prior therapies (unless resolved to  $\leq$  Grade 1).
7. Uncontrolled active infection.
8. Known positive for HIV or infectious hepatitis, type A, B or C.
9. Current use of monoamine oxidase A and B inhibitors (MAOIs).
10. Evidence at the time of screening of increased risk of bleeding, including any of the following:
  - o Activated partial thromboplastin time (aPTT)  $> 1.3 \times$  the upper limit of normal
  - o International normalized ratio (INR)  $> 1.3 \times$  the local upper limit of normal
  - o Known Acquired Von Willebrand's disorder.

#### **5.5 Guidelines**

These guidelines are for use by the Investigator, study staff and patient to safeguard patient safety while maintaining data integrity.

1. In general, supportive care (transfusions, administration of anti-fungals, etc.) should be maintained in accordance with institutional policy. Additionally:
  - a. It is advised that patients with a platelet count  $\leq 10 \times 10^9/L$  (10,000/ $\mu$ L) be transfused.
2. Patients taking medications that have the potential to induce or inhibit CYP3A4 or CYP2D6 should be monitored closely for potential effects of co-administration; particular attention should be given to anti-infectives in the azole class.
3. Cessation of IMG-7289 is invariably associated with a rebound in thrombopoiesis and platelet counts may easily exceed the baseline value. When IMG-7289 is discontinued, the platelet count should be monitored closely and an alternative cytoreductive therapy to lower platelets should commence within 24-48 hours.

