**Table 1: Titration and Re-challenge Rules**

Titration and Re-challenge Rules				
Hematology Assessment		Titration and Re-challenge Rules		
Plt Count ( $\times 10^9/\text{L}$ )	Hb Level (g/dL)	Titration?*	Titration Rule*	Re-challenge Rule*
$> 400$	$\geq 10$	Up-titrate □	Increase by 0.2 mg/kg/d □	N/A
$\geq 200$ to $\leq 400$	$\geq 10$	Maintain current dose	N/A	N/A
50-199	$\geq 10$	Down-titrate	Decrease by 0.1 mg/kg/d	N/A
N/A	8.5 to <10	Down-titrate	Decrease by 0.15 mg/kg/d	N/A
< 50	< 8.5	HOLD DOSE □	N/A	At 50% of prior dose** when: - platelets return to $\geq 100$ - Hb returns to $\geq 8$ ***

□Up-titration may begin on ITP Day 29 and occur no more frequently than every 4 weeks from the previous up- or down-titration. Down-titration can be made at any time in the best interest of the patient.

\*Patients requiring a dose hold should have complete blood counts monitored at least weekly for safety purposes and to enable re-challenge to commence as soon as counts return to the required level, if safe to do so.

\*\*The PI may, upon review of individual patients and patient responses, recommend up- or down-titration that are not in concordance with the above.

\*\* Re-challenge at 50% of the previous mg/kg dose.

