#### 6.5.1 Hematologic Toxicities

Hematologic values outside of the normal reference range are inherent features of MPNs and are expected effects of many therapeutic attempts to manage these diseases.

Both genetic knockdown (KD) of LSD1 mRNA and pharmacologic inhibition of LSD1 show that the loss of LSD1 activity arrests the production of mature red cells, platelets and granulocytes while over-producing monocytes ([Sprussel et al., 2012](#); [Kerenyi et al., 2013](#)). Production of cells of lymphoid lineage, B and T cells is unimpaired indicating that LSD1 has very cell-specific functions and its inhibition also has very specific effects. LSD1 inhibition in malignant myeloid cells causes the induction of monocytic differentiation markers, as well as a reduction of self-renewal potential of neoplastic cells, all of which eventually result in apoptosis of treated cells. Thus, the anemia, thrombocytopenia, neutropenia and monocytosis attending LSD1 inhibition, as observed in animals treated with IMG-7289, reflect primary pharmacodynamic effects. The kinetics of anemia, thrombocytopenia, and neutropenia following complete LSD1 inhibition are a function of the lifespan of the individually affected cell types. Over the course of LSD1 inhibition, platelet and neutrophil counts are the most affected, reflecting their short mean lifespans of approximately seven and twelve days, respectively. Recovery of peripheral counts is reversible, rapid, and temporarily overshoots baseline hematologic values. At lower doses, the effects on hematopoiesis are much less pronounced suggesting that a modicum of residual LSD1 activity is sufficient to support blood cell formation. Thus, both the duration of LSD1 inhibition as well as the degree of inhibition are critical to the pharmacodynamic effects on myeloid lineages.

The intended dosing plan for ET patients is predicated on the observation that inhibition of LSD1 has a therapeutic effect when LSD1 is inhibited for a fraction of the 24-hour dosing cycle. The concentrations of IMG-7289 needed to achieve maximal effects on growth, differentiation, and apoptosis in vitro with primary

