### 6.5.2 Dose Limiting Toxicities

DLT is defined as any one of the following AEs per CTCAE version 5.0 criteria that occurs through Day 7 of the Initial Treatment Period will be considered DLTs unless the Investigator deems the AE to be clearly unrelated to IMG-7289:

- Any Grade 3 or above thrombocytopenia associated with clinically significant bleeding\*;
- Any Grade 4 thrombocytopenia associated with a requirement for platelet transfusion;
- Any Grade 4 or 5 non-hematologic adverse event;
- Any Grade 3 or above non-hematologic adverse event with the following exceptions:
  - Nausea, vomiting or diarrhea lasting 3 days or less
  - Aesthenia lasting less than 7 days
- Any Grade 3 electrolyte abnormality unrelated to the underlying malignancy and persisting greater than 24 hours.

*\*A clinically significant bleeding event is defined as an event that is life-threatening, cannot be controlled and/or results in hemodynamic instability.*

Patients who experience DLT will have their dose adjusted downward by 50% if the Principal Investigator deems it safe for the patient to continue on IMG-7289; the titration rules will subsequently be followed. Any patient that experiences DLT that results in discontinuation of IMG-7289 therapy may begin alternative therapy within 24-48 hours of discontinuation if their physician deems this safe and appropriate regarding the resolution of the DLT.

Please consult the Principal Investigator for IMG-7289 dose modifications for the management of clinically significant changes in platelets, neutrophil counts, or other hematologic parameters.

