### 6.5.3 Stopping Rules

IMG-7289 will be discontinued in the event of the following:

- Post DLT, the Investigator deems it unsafe for the patient to continue on IMG-7289.
- Post dose reduction due to DLT, the patient either worsens at any time or fails to demonstrate significant improvement within 14 days.
- Post temporary interruption of IMG-7289 due to platelet counts below  $50 \times 10^9/L$  (50,000/ $\mu L$ ), the patient's platelet counts don't return to  $> 150 \times 10^9/L$  (150,000/ $\mu L$ ) within 21 days.
- Any Grade 4 non-hematologic adverse event with failure to recover to Grade 3 within 7 days of drug cessation.

Patients who discontinue IMG-7289 will enter follow-up assessments beginning with EoT visit.

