### 6.5.4 Interruption of Dosing

Patients requiring a Dose Hold according to the Titration and Rechallenge Rules, or due to an (S)AE, should be monitored at least weekly for safety purposes and to enable re-challenge to commence as soon as counts

return to the required level, if it safe to do so. During these visits, patients are required to undergo complete blood counts only.

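### Section 5.5 item 3 tells sites to start platelet-lowering therapy within 24-48 hours of any discontinuation, with no exception for a patient stopped under Section 6.5.3 because platelets stayed too low

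*Combined protocol and SAP*

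**What the plan says.** Section 5.5 item 3 and the synopsis Guidelines give the same instruction and the same reason. The reason is that "Cessation of IMG-7289 is invariably associated with a rebound in thrombopoiesis", with counts that may exceed baseline. The instruction is to monitor platelets closely and that "an alternative cytoreductive therapy to lower platelets should commence within 24-48 hours". Neither copy gives a platelet threshold or distinguishes between reasons for stopping.

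Section 6.5.3, copied in the synopsis Stopping Rules, lists a stop that begins "Post temporary interruption of IMG-7289 due to platelet counts below" 50 x 10^9/L. It applies when the count has not returned above 150 x 10^9/L within 21 days. The patient then goes to follow-up starting with the End of Treatment visit, and item 3 is neither waived nor qualified.

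Section 6.5.2 uses softer wording for DLT stops: the patient "may begin alternative therapy within 24-48 hours of discontinuation if their physician deems this safe and appropriate regarding the resolution of the DLT". The synopsis paragraph on DLTs also says *may*, but without the physician condition.

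**The concern.** One of the protocol's required stops is defined by platelets that are too low and have not recovered. The general guideline for what follows a stop is to lower platelets. The justification for that guideline is rebound after drug withdrawal. A patient who has been off drug for the whole 21 days and still meets the stop has not shown that rebound.

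Followed as written, item 3 would add platelet suppression in a patient who is still thrombocytopenic. Section 5.5 is meant to protect patients and is addressed to staff and patients as well as the investigator, so it should be safe to follow literally.

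**Working it through.** No sample-size or power figure is involved. The check sets the rules side by side and follows one patient through them.

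**Inputs**
- Hold: platelets below 50 x 10^9/L (Table 1; Section 6.5.3).
- Re-challenge: "At 50% of prior dose when: - platelets return to" at least 100 and hemoglobin is at least 8 g/dL (Table 1). Section 6.5.4 adds that held patients "should be monitored at least weekly for safety purposes and to enable re-challenge to commence as soon as counts" allow.
- Stop: not above 150 within 21 days (Section 6.5.3).
- Platelet lifespan about 7 days: Section 6.5.1 describes platelets and neutrophils as "reflecting their short mean lifespans of approximately seven and twelve days, respectively".

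**Step 1: count at the stop.** By the stopping rule the count is 150 or less, against a titration target of 200 to 400. If the patient was never re-challenged, it is normally below 100, because reaching 100 would have opened re-challenge. The exception is a count of 100 to 150 with re-challenge withheld because hemoglobin was below 8 or restarting was judged unsafe.

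**Step 2: time off drug.** Assume that the hold starts right after the last dose and no drug is given in the 21 days. Then 21 days / 7 days = 3 platelet lifespans off drug. Section 6.5.1 expects otherwise: "Recovery of peripheral counts is reversible, rapid, and temporarily overshoots baseline hematologic values". In this patient that recovery has not occurred.

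**Step 3: what item 3 then asks.** Section 6.5.3 separates a temporary interruption from a discontinuation, so I take the 24-48 hours to run from the decision to discontinue. Platelet-lowering therapy would then start one to two days after a count of 150 or less. Counting from the last dose does not help: the window would then fall at the start of the hold, just after a count below 50.

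**Step 4: is there an exception elsewhere?**
- Section 6.5.2 has a suitable condition, but only for discontinuations resulting from a DLT. A DLT is dated by when the event occurs, through Day 7. A hold for an early event that meets a thrombocytopenia DLT criterion is therefore covered, whenever the stop itself falls. A hold triggered after Day 7 is not.
- The notes to Table 1 (consult the PI), Section 7 (unscheduled visits) and the Section 11 reporting requirements (contact the drug supplier's medical staff) say who decides or when to see the patient. None states an exception to item 3.
- Section 5.6 item 4 bars anticoagulants and NSAIDs below 50 x 10^9/L. The protocol sets a platelet floor there; item 3 has none.

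**Step 5: patients back on half dose at the stop.** Someone re-challenged at 100 or more can still miss the 150 mark by day 21. Drug withdrawal is then recent and rebound may lie ahead, so early cytoreduction is arguable. The misfit in Steps 1 to 3 does not extend to them.

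**The case against.** The strongest reply is that item 3 is an advisory *should* in a section headed as guidelines. It is paired with close platelet monitoring, and a therapy meant to lower platelets presupposes a count that needs lowering. It reads most naturally for a patient whose last dose and discontinuation coincide. Significant platelet changes go to the PI, and an investigator would probably not apply the line mechanically. The group may also be empty: entry requires platelets above 450, Table 1 down-titrates at 50 to 199 before a hold, and recovery is expected to be rapid. All of this stands and keeps the point minor. It does not supply the missing exception.

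A reader might go further in three ways that the documents do not support.
- That a stop under this bullet can never be a DLT stop because it comes weeks after Day 7. The DLT definition turns on the date of the event, so that comparison shows nothing.
- That cytoreduction should be barred at or below 150 and started above it. The 150 is a recovery mark in a stopping rule, not a treatment threshold. Table 1 still reduces drug at 50 to 199, and a fixed bar could hold back a patient who is rising quickly and was enrolled because of thrombotic risk.
- That item 3 is wrong for every stop under the platelet bullet. Patients on half-dose re-challenge are a different case.

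**Conclusion.** The gap is real and minor. Item 3 contains no exception for the 6.5.3 platelet stop, and the nearest safety condition covers only stops caused by a DLT. In the clearest case, a patient never re-challenged, the literal instruction applies at 150 x 10^9/L or less, normally below 100, about 3 platelet lifespans after the last dose.

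This rests on the 24-48 hours running from the discontinuation decision and on the hold lasting the full 21 days without drug. The documents give no frequency for this group. With at most 20 patients and rapid recovery expected, it is probably rare. The Week 24 complete remission endpoint and the Simon boundaries (1 or fewer of 9; 4 or fewer of 20) are unaffected.

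**What to change.** In both copies of item 3 (Section 5.5 and the synopsis Guidelines), add a sentence to this effect: *For discontinuation under the 6.5.3 platelet criterion, the 24-48 hour default does not apply; continue CBCs at least weekly, and begin alternative cytoreductive therapy only when the physician judges it safe and appropriate given the current platelet count and trend.* This extends the principle of Section 6.5.2 and sets no fixed starting count. It also leaves room for early treatment of patients who were on re-challenge dosing.

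Separately, for DLT stops, align the *should* in both copies of item 3, and the unconditional *may* in the synopsis DLT paragraph, with Section 6.5.2.

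Cost: one sentence in two places and a wording alignment, with no added patients. For a patient off drug since the hold began, the End of Treatment visit (about day 21) and the End of Study visit (day 28 after the last dose) already include CBCs. Weekly counts beyond those add 0 if platelets recover by day 28, 2 if by day 42 (days 35 and 42), and 4 if by day 56 (days 35, 42, 49 and 56). That recovery range is my assumption, and monitoring is open-ended until recovery. Item 3 already asks for close monitoring, so part of this is not new. The downside is that cytoreduction could start up to about 7 days later if rebound is fast and falls between weekly CBCs.
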